Statistical Analysis Plan

Developing a deliberate practice intervention to recalibrate physician heuristics in trauma triage

NIA R21AG072072

Clinicaltrials.gov identifier #NCT05168579

November 25, 2022

Assessment framework

We used Proctor's Framework of Implementation Outcomes in Research to structure our process assessment of the novel intervention. We defined the implementation outcomes as feasibility, fidelity, acceptability, adoption, and appropriateness. Using the NIA's Stage Model of Intervention Development which recommends assessment of efficacy in the laboratory before moving to real-world testing, we defined the service outcome (efficacy) as compliance with clinical practice guidelines, measured using simulation.

Data sources and management

Screening questionnaire and tracking database

Each respondent completed a questionnaire with items on their age, sex, race, ethnicity, and educational background at the time of enrollment. We maintained a database with a list of scheduled coaching sessions, which was updated daily with the status of the sessions.

Coaching sessions

We recorded all the coaching sessions and automatically uploaded them to a secure server hosted by the University of Pittsburgh. Two members of the study team ([name], [name]) developed a codebook to assess the delivery of core session components, refined it until they achieved acceptable inter-rater reliability (Cohen's kappa 0.84), and independently applied it to the recordings. Coding discrepancies were resolved through consensus ([name], [name], DM). We used NVivo qualitative analysis software (QSR International, Melbourne, Australia) for data management.

Post-intervention debriefing materials

Participants in the intervention group provided structured assessments of the acceptability of the intervention using the User Engagement Scale—Short Form to evaluate the video game (a validated 12-item instrument with a 5-point Likert scale), and the Wisconsin Surgical Coaching Rubric to evaluate the quality of the coaching (a 4-item instrument with a 5-point scale). They also participated in semi-structured debriefing interviews after the final coaching session, during which they discussed their perception of the acceptability, adoption, and appropriateness of the intervention. Two members of the study team ([name], [name]) developed a codebook, refined it until they achieved an acceptable inter-rater reliability (kappa 0.84), and independently applied it to transcripts of the interviews. Any coding discrepancies were resolved through consensus ([name], [name], DM).

Simulation to measure efficacy

We used a validated 2-D simulation to assess changes in physician behavior after exposure to the intervention (i.e., compliance with clinical practice guidelines). The simulation required participants to respond to 10 cases over 42 minutes: 4 severely injured patients, 2 minimally injured patients, and 4 critically ill non-trauma patients. New patients arrived at pre-specified but unpredictable intervals, so that users managed multiple patients concurrently. Without appropriate clinical intervention by the player, severely injured patients and critically ill distractor patients decompensated and died over the course of the simulation. Each case included a 2-D

rendering of the patient, a chief complaint, vital signs which updated every 30 seconds, a history, and a written description of the physical exam. Users could request more information by selecting from a pre-specified list of 250 medications, studies, and procedures. They could place orders, and consult specialty services. Each case ended when the player either made a disposition decision (admit, discharge, transfer) or the patient died.

We asked all trial participants to complete the simulation online, and responses were uploaded and stored on a secure server hosted by the University of Pittsburgh.

Analyses

We summarized physician characteristics using means (standard deviations [SD]) for continuous variables and number (%) for categorical variables. We analyzed implementation outcomes using an intention-to-treat approach, but excluded from the efficacy analysis participants who did not use the simulation. We had two criteria for the success of the trial: efficacy and feasibility. Our primary hypothesis was that physicians exposed to the intervention would under-triage $\geq 25\%$ fewer patients on the simulation than physicians in the control arm. Our secondary hypothesis was that $\geq 90\%$ of participants would receive all three coaching sessions.

Implementation outcomes

We quantified the proportion of coach-participant dyads that completed three thirty-minute sessions (to measure feasibility), and summarized the proportion of core components delivered to participants (to measure fidelity). We summarized participant responses to the User Engagement Scale-Short Form and to the Wisconsin Surgical Coaching Rubric (to measure acceptability). We also summarized themes that arose during the semi-structured interviews (to further assess acceptability and to assess appropriateness and adoption).

Efficacy

We summarized time spent and decisions made for each severely injured trauma case on the simulation (e.g., diagnostic testing, administration of blood products), and scored disposition decisions as consistent with the American College of Surgeons guidelines or not. To compare differences between the intervention and control groups, we used generalized linear models, clustered at the participant level. In a post-hoc sensitivity analysis, we excluded physicians who had previously participated in our research.

Human subjects and power calculation

We designed the experiment to detect a 25% (large effect size) reduction in under-triage between physicians in the intervention and control groups, with an alpha of 0.05 and a power of 80%, using Cohen's method of estimating power for behavioral trials. Based on these estimates, and anticipating a 67% retention rate in the control arm, we planned to recruit 30 physicians for each arm.

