We will summarize the proportion of coach-trainee dyads that complete all the training sessions. To deem the intervention delivery strategy feasible, we will need to see $\geq 90\%$ protocol adherence. We will also summarize the characteristics of game use by each trainee, including whether any of them use the game outside the deliberate practice sessions; assessments of coaching performance by independent raters and by trainees; assessments made by coaches of intervention receipt. Finally, we will perform a series of exploratory analyses using non-parametric tests (Fisher exact test, Wilcoxon-Mann Whitney, Kruskal Wallis, repeated measures regression models) to characterize the association between trainee characteristics and: a) protocol adherence; b) coaching skill (first session and overall); c) intervention receipt (first session and overall).

Aim 2. To assess the potential effect size of the intervention.

Ha2: We will detect a large difference in the diagnostic errors made by trainees and control physicians.

We will use the virtual simulation to assess physician diagnostic performance, and will use an intention-to-treat approach (i.e. all trainees regardless of whether they completed all the sessions will be asked to use the simulation). We will measure the proportion of severely injured patients appropriately triaged to a trauma center as per the American College of Surgeons guidelines. We will estimate both the group mean of diagnostic errors made by trainees and passive control physicians, and variability in the group-specific outcome. We will use a Students' t-test to compare the means of the two groups. To deem the intervention successful (and worth pursuing), we will need to detect a large difference (~25%) between the two groups. In exploratory analyses, we will also assess the effect of the intervention on heuristics by studying patterns of errors (as we have done previously). We will not test any mediators of efficacy because of the sample size.

Aim 3. To assess the acceptability of the intervention.

We will summarize responses to the User Engagement Scale-Short Form. We will also use best practice methods to report qualitative results from the semi-structured interviews, focusing on participant perceptions of the effect of the intervention on engagement.

Power analysis

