We will assess the feasibility of using deliberate practice to recalibrate physician heuristics including barriers to implementation, fidelity, acceptability, the magnitude and variance of the treatment effect. We anticipate that $\geq 80\%$ of physicians in both the trainee and control groups will complete the virtual simulation. Based on Cohen's power estimates for behavioral trials, with at least 20 physicians in each group, we can detect a large difference (0.80 standard deviation) in their performance, using a t-test, with power of 80% and alpha=0.1.73 Given the distribution of responses in the past, this would manifest as a 25% difference in diagnostic error.

Consent Process

Process

We will email physicians describing the study and ask if they are interested in participating. The email will include a link to a Qualtrics survey that hosts a more detailed description of the study, a consent form, and a demographics questionnaire. Once physicians have consented to participate in the trial, they will be randomized to the intervention or passive control arm.

Steps to minimize coercion

Physicians will be given three days to respond to the email, at which point they will receive a reminder. Physicians who do not respond within 1 week to the recruitment email will not be contacted further. To minimize coercion, the Qualtrics document will emphasize that participation is voluntary, and consent can be withdrawn at any point during the study.

Ongoing consent

The study will involve multiple rounds of coaching (three in total), for those assigned to the intervention arm. The study coordinator will ensure ongoing consent when scheduling followup coaching sessions.

Steps to be taken to ensure the subjects' understanding

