4. Only limited team members will have access to personal information needed for tracking and informed consent. No personal information concerning study participants will be released without their written consent.

Foreseeable Benefits: coaching has the potential to improve physicians' performance and enhance their skill set.

Subject withdrawal from study: if physicians withdraw from the study after partial completion of the study tasks, we will analyze their residual data. In particular, understanding reasons for their withdrawal are extremely important for achieving the study objectives (assessing the feasibility of using deliberate practice interventions).

Project Timeline

Table 2. Overview of study tasks and planned timing

Task	4-7 2021	8-10 2021	11 2021	12 2021	1-4 2022	5/22- 3/23
Complete regulatory tasks (e.g., set up contracts, file IRB)	x					
Modify Shift with Friends		x				
Standardize coaching skill of team members			x			
Recruit and randomize a national sample of physicians				x		
Completion of study tasks: deliberate practice sessions, virtual simulation, assessment					x	
Analysis of data					x	x

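### The protocol's efficacy test is a t-test, but the later SAP replaces it without explanation by an under-specified participant-clustered GLM, and alpha also differs between the two documents

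*SAP*

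**What the plan says.** **Protocol, Primary and secondary study endpoints, Aim 2.** Diagnostic performance is measured on the simulation, group means and variability are estimated, and the test is named: "We will use a Students' t-test to compare the means of the two groups". Success is judged by a difference of about 25% between arms.

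**Protocol, Power analysis.** At least 20 physicians per group and a difference of 0.80 SD, "using a t-test, with power of 80% and alpha=0.1.73". I read the trailing 73 as a citation number, so alpha is 0.1. Sidedness is not given.

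**Protocol, Project Timeline, Table 2.** The row "Completion of study tasks: deliberate practice sessions, virtual simulation, assessment" is marked for January to April 2022. Analysis runs from then to March 2023.

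**SAP, title block.** Dated "November 25, 2022".

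**SAP, Analyses, Efficacy.** Disposition of each severely injured case is scored against the guidelines. The comparison is then described: "To compare differences between the intervention and control groups, we used generalized linear models", with clustering by participant. The t-test is not mentioned. The SAP's power paragraph gives alpha 0.05 and 80% power, again without sidedness, and names no test.

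**The concern.** The efficacy test should be identifiable before the outcome data are examined. Here the protocol points to one test and the SAP to a family of models. The link is open, and it decides whether the result is a risk difference, a risk ratio or an odds ratio. Only some of these can be set directly against a criterion of 25% fewer under-triaged patients.

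The SAP also raises the weight of this comparison. The protocol's Study Aims label adherence the primary outcome, whereas the SAP makes under-triage its primary hypothesis. So the re-specified test carries the trial's main claim, in a document dated some seven months after the planned end of the simulation period, with no statement of when or why the model was chosen.

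Three things could be affected: the credibility of the test as pre-specified, its actual error rate, and the power that can be claimed for it.

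**Working it through.** **1. The plan's own power figure.** Inputs (Protocol, Power analysis): 20 per group, d = 0.80, alpha 0.1. The noncentrality is d × √(n₁n₂/(n₁+n₂)) = 0.80 × √(400/40) = 2.53, with 38 degrees of freedom.
- Two-sided 0.1 (critical value 1.686): power 79.9%. The stated 80% reproduces.
- Two-sided 0.05 (critical value 2.024): power 69.3%. Reaching 80% needs 26 per group.
- One-sided 0.05: 79.9%, the same as two-sided 0.1.
- The SAP's retention figure reproduces the recruitment target: 20/0.67 = 29.9, so 30 per arm. If all 30 trainees and 20 controls finish, the noncentrality is 0.80 × √(600/50) = 2.77 and power at two-sided 0.05 is 77.5%.

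The SAP's 0.05 with 80% power therefore agrees with the protocol's 0.1 only if the SAP's test is one-sided, and neither document says so.

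**2. How far the two tests differ.** Suppose all 4 severely injured cases (SAP, Simulation to measure efficacy) are scored for every physician. A GLM with identity link and independence working correlation then estimates the difference in mean physician proportions, which is the contrast the t-test uses. Its uncorrected robust variance per arm is s²/n × (n−1)/n. With n = 20 the standard error is multiplied by √(19/20) = 0.975, so a z cut-off of 1.96 acts like 1.96 × 0.975 = 1.91 on a t statistic with 38 df. The two-sided tail is then about 6.4% instead of 5%.

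**3. Error rates by simulation.** The documents give neither the under-triage rate nor the within-physician correlation. Assumed: rates 0.40, 0.60 and 0.75; ICC 0, 0.1 and 0.3 (beta-binomial); 4 cases per physician; arms of 20/20, 24/24 and 30/20; no true effect; two-sided 0.05; 40,000 trials per setting (Monte Carlo standard error √(0.05 × 0.95/40,000) = 0.11 points).

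| Test | Type I error |
|---|---|
| t-test on physician proportions | 4.8–5.2% |
| Clustered, identity link, t reference | 5.1–5.6% |
| Clustered logistic, G/(G−1) factor | 5.2–5.8% |
| Clustered logistic, no correction, z | 5.4–6.0% |
| Clustered, identity link, no correction, z | 6.0–6.6% |
| Better of t-test and clustered logistic | at most about 6.1% |
| Clustering ignored, ICC 0.1 / 0.3 | 8–9% / 15–16% |

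G is the number of physicians.

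**4. Why the link matters.** If a logistic model were used and an odds ratio of 0.75 were read as 25% fewer, then for an assumed control under-triage rate:
- 40%: odds 0.667 × 0.75 = 0.50, risk 33.3%, a relative reduction of 17%.
- 60%: odds 1.5 × 0.75 = 1.125, risk 52.9%, a reduction of 12%.
- 75%: odds 3 × 0.75 = 2.25, risk 69.2%, a reduction of 8%.

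A true 25% relative reduction from 60% (to 45%) is an odds ratio of (0.45/0.55)/1.5 = 0.55. The same result could be read as meeting or missing the criterion, depending on the scale.

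**The case against.** A participant-clustered GLM is a legitimate analysis of several binary decisions per physician, and it avoids the serious error of treating cases as independent. The SAP names one model, and its only alternative analysis is labelled post hoc. The protocol judges success by the size of the difference, not by a p-value, which limits the effect of small error-rate changes in a pilot. All of this stands.

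Four stronger readings are tempting, and the documents do not support them:
- *The SAP's test runs above its nominal level.* The SAP states no variance estimator or reference distribution, so no single error rate can be assigned to it. The excess ranges from almost nothing to about 1.6 points.
- *Two available tests nearly double the error rate.* The independent-tests figure, 1 − 0.95² = 9.75%, does not apply. Both tests use the same data and nearly always agree, and no passage permits both as primary.
- *The power statement does not describe the SAP's test.* With an identity link and four scored cases each, the contrast is the same and power is essentially unchanged. The power problem is alpha.
- *The model was chosen after seeing the results.* Table 2 gives planned dates only. The past tense and the achieved kappa values in the SAP show late writing, not when the model was chosen.

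What remains is an unexplained change to a model that cannot be reproduced from its description.

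**Conclusion.** The point holds as a matter of pre-specification. The efficacy test differs between protocol and SAP, the replacement is under-specified, no reason is given, and the SAP is dated after the planned simulation period. Whether outcomes had been seen cannot be settled from these documents.

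The direct effect on the error rate is small: about 5.1–5.8% with a common correction, up to about 6.6% without one, and about one point at most from choosing between the t-test and the logistic GLM. These figures rest on the assumed rates, ICCs and arm sizes. Further freedom, such as covariates or sidedness, could add to this, but the documents give no basis for sizing it.

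The unreconciled alpha matters more. At 20 per arm and 0.80 SD it moves power by 79.9 − 69.3 = 10.6 percentage points. That rests on reading the protocol's alpha as 0.1 and on both tests being two-sided.

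**What to change.** 1. Report the protocol's analysis as the pre-specified result: each physician's proportion of the 4 severely injured cases under-triaged, compared by t-test, with the difference and its confidence interval.
2. Present the clustered GLM beside it. State whether the 25% criterion is absolute or relative and use a link that gives that measure directly (identity for a difference, log for a ratio). Use a small-sample-corrected robust variance and a t reference distribution.
3. Disclose when and why the GLM was added, and whether outcome data were available at that time.
4. Reconcile alpha (0.1 or 0.05), state sidedness, and give the power that follows.

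The cost is SAP wording and one extra line of output. No new data are needed. The p-value may become slightly less favourable, and if alpha is two-sided 0.05 the 80% power claim at 20 per arm must be lowered.

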At the time of enrollment, we will ask both trainees and passive control physicians to complete a questionnaire that surveys their personal characteristics (time required: 10 minutes). Trainees will be assigned a coach, and will be asked to schedule weekly 30-minute meetings for three weeks, at which time they will play a video game and will receive feedback on how to use best-practice triage decision principles (time required: 90 minutes). Trainees will also be asked to complete a short assessment of their coaches' performance after each session (time required: 5 min/session). After completion of the intervention, trainees will be scheduled to participate in a semi-structured debriefing interview (time required: 20 minutes). Both trainees and passive-control physicians will be asked to complete a virtual simulation that assesses their triage decision making (time required 42 minutes). Trainees will therefore spend 3 hours completing study tasks; passive control physicians will spend 1 hour. Trainees will receive an iPad with the video game pre-loaded at the time of enrollment. They will keep the iPad as their honorarium for participating in the study. Passive control physicians will receive a \$100 gift card as a fixed, wage-based honorarium for participating in the study. We chose to provide the honorarium to minimize attrition and to ensure completion of study tasks. Based on our prior experience, the combination of framing participation as altruistic, e-mail reminders about completion of study tasks, and provision of a wage-based, fixed honorarium increases completion rates to as high as >80%. Given the costs of running a trial, and bias introduced by differential completion of study tasks, we believe that using an honorarium is warranted.

Sources of data

Physician self-report

1. Physician characteristics. We will ask all participants to respond to a questionnaire that asks about personal characteristics: demographics (e.g. age, sex, race), training (e.g. name of medical school, name of residency training program and fellowship [if applicable], year of board certification), professional experience (e.g. years in practice, number of shifts worked/month, number of patients treated/shift), and practice environment (e.g. trauma center designation of hospital; resource availability).

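### For the same 25% effect and 80% power the protocol states alpha 0.1 and the SAP 0.05, neither with sidedness; if 0.05 is two-sided, power is about 73% to 78%

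*SAP*

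**What the plan says.** **Protocol, Power analysis.** The protocol states that "with at least 20 physicians in each group, we can detect a large difference (0.80 standard deviation) in their performance", using a t-test with 80% power and alpha 0.1. It equates this to a 25% difference in diagnostic error. It expects that at least 80% "of physicians in both the trainee and control groups will complete the virtual simulation". Under Research activities it says that its approach to honoraria and reminders "increases completion rates to as high as >80" percent.

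**SAP, Human subjects and power calculation.** The SAP states a design to detect a 25% reduction in under-triage, labelled a large effect size, "with an alpha of 0.05 and a power of 80" percent, "using Cohen's method of estimating power for behavioral trials". It continues: "anticipating a 67% retention rate in the control arm, we planned to recruit 30 physicians for each arm". It gives no retention figure for trainees, no standard deviation and no test for this calculation.

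**SAP, Analyses.** The primary hypothesis is that the intervention arm under-triages at least 25% "fewer patients on the simulation than physicians in the control arm". The authors "excluded from the efficacy analysis participants who did not use the simulation". The Efficacy section specifies generalized linear models clustered at the participant level.

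Neither document says whether its alpha is one- or two-sided.

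**The concern.** Both documents appear to describe one design: 30 per arm, about 20 analysable controls, a 25% effect called large, 80% power and Cohen's method. The outcome labels differ (diagnostic error and under-triage). However, Aim 2 of the protocol measures diagnostic performance as the proportion of severely injured patients triaged appropriately, so the target is essentially the same.

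Halving alpha at an unchanged sample size, effect and sidedness must lower power, yet both documents report 80%. Either the sidedness differs between them without being stated, or the SAP's 80% is too high.

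What is at stake is how a non-significant efficacy result is read. A reader who takes 0.05 as two-sided will assume a 20% chance of missing a true large effect. Efficacy is the SAP's primary hypothesis, and the protocol says the study will inform a later Stage III trial.

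**Working it through.** **Inputs**
- Effect: 0.80 SD (protocol, Power analysis). Carrying it over to the SAP is an assumption.
- Test: two-sample t-test (protocol, Aim 2 and Power analysis).
- Alpha: 0.1 (protocol) and 0.05 (SAP). The digits 73 directly after the protocol's 0.1 are read as a citation number.
- Controls: 30 × 0.67 = 20.1, about 20 (SAP). At the protocol's 80% floor: 30 × 0.80 = 24.
- Trainees: at least 24 (protocol floor), up to 30 if all complete. The SAP gives no figure.
- Completers are the right count, because the SAP drops non-users of the simulation from the efficacy analysis.

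**Formula.** With n1 trainees and n2 controls, the noncentrality is 0.80 / √(1/n1 + 1/n2), with n1 + n2 − 2 degrees of freedom. Power is the probability that a noncentral t variable passes the critical value (either tail, if two-sided).

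**Step 1: reproduce the stated 80% at 20 per group.** Noncentrality = 0.80 / √(1/20 + 1/20) = 2.530, with 38 degrees of freedom.

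| Reading of alpha | Critical t | Power |
|---|---|---|
| 0.10 two-sided | 1.686 | 79.9% |
| 0.05 one-sided | 1.686 | 79.9% |
| 0.05 two-sided | 2.024 | 69.3% |
| 0.10 one-sided | 1.304 | 88.9% |

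The protocol's 80% reproduces if its 0.1 is two-sided. The SAP's 80% at 20 per group reproduces if its 0.05 is one-sided. These two readings share a critical value and are in effect one calculation.

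**Step 2: the SAP's alpha read as two-sided 0.05, at the documents' retention figures.**

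| Trainees / controls | Source of counts | Noncentrality | Power | Chance of missing 0.80 SD |
|---|---|---|---|---|
| 24 / 20 | protocol floor / SAP 67% | 2.642 | 73.3% | 26.7% |
| 24 / 24 | protocol floor in both arms | 2.771 | 77.4% | 22.6% |
| 30 / 20 | all trainees complete / SAP 67% | 2.771 | 77.5% | 22.5% |
| 20 / 20 | protocol's minimum group size | 2.530 | 69.3% | 30.7% |

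**Step 3: where the shortfall ends.** At two-sided 0.05, 80% needs 26 completers per arm (80.7%; 25 gives 79.2%). With all 30 trainees it needs 23 controls (80.8%), which is 23/30 = 77% control retention against the SAP's 67%. With 30 trainees and 24 controls power is 81.8%, and with 30 and 30 it is 86.1%.

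**Step 4: detectable effect** for 80% power at two-sided 0.05: 0.87 SD at 24/20, 0.83 SD at 24/24 or 30/20, and 0.91 SD at 20/20.

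**Not computable.** The power of the SAP's clustered model needs a baseline under-triage rate and a within-participant correlation. Neither document gives them.

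**The case against.** The strongest reply is that nothing has been miscalculated. Two-sided 0.10 and one-sided 0.05 give the same 79.9% at 20 per group, and both documents word the hypothesis in one direction. That stands as far as it goes: the SAP's 80% may be correct. But no one-sided test is declared in either document, and a directional hypothesis does not declare one. A reader therefore cannot tell which reading applies, and the change of alpha is unexplained.

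Three further points limit the size of the concern, and all stand.
- The 69.3% figure requires losing 10 of 30 trainees. The protocol expects at least 80% completion in both arms, and the SAP anticipates loss only among controls. So 69.3% belongs to the protocol's minimum group size and is not a forecast.
- The 0.80 SD and the t-test come from the protocol. The SAP prints neither for this calculation and analyses with a clustered model, so the percentages are approximations.
- This is a 60-physician pilot whose success criteria, about a 25% difference and 90% session completion, cite no alpha.

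A reader might go further and infer that the trial is underpowered. The documents do not support that: it requires a two-sided reading that they never state, and retention better than they assume removes the shortfall.

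A reader might also infer that alpha was changed after the data were seen, because the SAP is dated November 2022 and the protocol scheduled the study tasks for January to April 2022. The dates show when the SAP was written. They do not show when or why alpha changed.

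**Conclusion.** The inconsistency holds and should be fixed: alpha 0.1 in one document and 0.05 in the other, for the same effect and the same 80% power, with sidedness in neither. This is a conflict in a stated design figure. It is not a demonstrated arithmetic error.

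The power shortfall is conditional. If the SAP's 0.05 is two-sided, and 0.80 SD and a t-test are carried over, the stated power is too high by 2.5 points (30/20) to 6.7 points (24/20). If the 0.05 is one-sided, 80% stands at 20 per group. Confidence is high in the mismatch and lower in the shortfall for the SAP's actual analysis, whose power is unknown. The effect is confined to interpreting a non-significant efficacy result.

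A related inconsistency belongs with it: the SAP's 67% control retention against the protocol's expectation of at least 80% in both arms.

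**What to change.** Change only the SAP power paragraph. Establish from planning records which alpha and sidedness were intended, state them, and reconcile them with the protocol's Power analysis section.

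- **(A) If the plan was the protocol's calculation**, write: *two-sided alpha of 0.10 (equivalently one-sided 0.05), 80% power for 0.80 SD with 20 completers per arm, t-test.* Explain any later change of alpha.
- **(B) If a two-sided 0.05 is kept**, replace the 80% with: *about 73% to 78% power by t-test approximation for 0.80 SD, with 20 controls and 24 to 30 trainees (69% at 20 per arm).* Add that power for the clustered model was not calculated.

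In either case, state the assumed trainee retention and reconcile the 67% control figure with the protocol's 80% or more in both arms.

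The cost is one paragraph of wording and a check of the records. Under (B) the stated power is slightly less favourable and remains an approximation to the model used. Enrolment, the analysis and the 25% criterion stay as they are.
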